Clinical laboratory parameters will be summarized across time points and changes from baseline will be summarized. The frequency of clinically significant abnormal laboratory values will be tabulated. Shift tables will be produced for selected laboratory parameters, including at least hemoglobin, WBC count, absolute neutrophil count, absolute lymphocyte count, platelet count, AST, ALT, total bilirubin, alkaline phosphatase, creatinine, and electrolytes. These tables will summarize the number of patients with each baseline CTCAE grade and changes to the maximum CTCAE grade on study.

Changes in vital signs parameters (i.e., systolic and diastolic blood pressures, pulse rate, respiration rate, and body temperature) will be summarized across time points, and changes from baseline will be summarized. Changes in ECG findings, PFTs, and pulse oximetry will be summarized, as appropriate, and by-patient listings will be provided. Serological findings, including Jo-1 and ADA Ab titers will be tabulated, and by-patient listings provided.

Additional safety analyses may be determined at any time without prejudice, in order to enumerate rates of toxicities most clearly, and to define further the safety profile of ATYR1940.

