9.3. Changes to the Planned Statistical Methods

Changes to the planned statistical methods will be documented in the clinical study report.

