1.1 Changes from Protocol

The ATYR1940-C-006 Protocol dated 22-Mar-2016 defines baseline as the following: For patients who received ATYR1940 \leq 4 weeks previously in the parent study, baseline refers to the baseline in the parent study (i.e., the most recent assessment obtained before the first study drug dose). For patients who received ATYR1940 >4 weeks previously in the parent study, baseline refers to assessment obtained before the first ATYR1940 dose at Week 1 in the current study.

However, the SAP defines baseline as the baseline in the parent study (ATYR1940-C-003 or ATYR1940-C-004) for all subjects enrolled in study ATYR1940-C-006.

The following changes/clarifications were provided for the schedule of events in Table 1 of the protocol:

- Plasma Biomarkers- Time points for Plasma Biomarkers were not specified in the protocol: During all dosing visits Plasma Biomarkers should be collected at infusion pre dose and 4 hours after the start of the infusion.
- Muscle Biomarker- Muscle Biomarkers are being completed at Week 14 in the 004 parent study; however, the 006 protocol says that these procedures will be completed in addition to Week 14 procedures. Muscle biomarkers are not completed in the 003 study: Muscle Biomarker should be drawn during the Week 1 visit in the 006 study for 003 patients only as patients in the 004 study will have muscle biomarkers collected at the Week 14 visit in the parent study, which occurs on the same day.
- Plasma Complement Factors- Plasma Complement Factors are requested to be collected during Week 1 in the 006 study; however, plasma complement factors are already being collected during the Week 14 visit in the parent study, which occurs on the same day: Collection of plasma complement factors is not required to be repeated during the Week 1 extension visit as noted in the Schedule of Events.
- Serum Complement & Tryptase Levels- Serum Complement & Tryptase Levels are requested to be collected during Week 1 in the 006 study; however, Serum Complement & Tryptase Levels are already being collected during the Week 14 visit in the parent study, which occurs on the same day: Collection of Serum Complement & Tryptase Levels is not required to be repeated during the Week 1 extension visit as noted in the Schedule of Events.

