8.3 Data Handling and Transfer

Data will be entered by investigational sites into a clinical database built with DataLabs version 5.0 and exported as SAS® version 9.4 or higher datasets (SAS Institute, Inc., Cary, NC). Converted datasets are created using SAS® and following Clinical Data Interchange Standards Consortium (CDISC) Standard Data Tabulation Model conventions (v3.1.2). Derived analysis datasets are generated using SAS® and following standard CDISC Analysis Dataset Model conventions (implementation guide v1.0). Data analyses including summary tables, figures, and listings (TFLs) are produced using SAS®.

Medical history and AEs will be coded using the Medical Dictionary for Regulatory Activities (MedDRA) version 18.1 to assign a system organ class (SOC) and preferred term (PT) to each AE. AE severity will be graded using Common Terminology Criteria for Adverse Events (CTCAE) version 4.03.

Prior and concomitant medications are coded to preferred drug names using the World Health Organization Drug Dictionary Enhanced (WHODRUG DDE, 2015SEP01).

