9.6.2 Laboratory Data

Laboratory data, including hematology, serum chemistry and urine analysis with microscopy, will be collected at Week 1 (if required) and monthly (Week 4, 8, etc) during the Treatment Period, and at 1-Week F/U, 4-Week F/U and 12-Week F/U during the Post-treatment Follow-up period. Additional safety lab assessments will be performed for patients with evidence of generalized IRR. These data will be listed, but not summarized. Table 2 details the parameters assessed.

TABLE 2. LABORATORY PARAMETERS

Hematology	Biochemistry	Urinalysis
Hematocrit	Aspartate aminotransferase (AST)	Color
Hemoglobin	Alanine aminotransferase (ALT)	Specific gravity
Red blood cell (RBC) count	Total bilirubin	Glucose
White blood cell (WBC) count	Insulin-like growth factor 1	Blood
Platelet count	Gamma-glutamyl transferase (GGT)	pH
Neutrophils	Alkaline phosphatase	Protein
Lymphocytes	Blood urea nitrogen	Ketones
Monocytes	Creatinine	Appearance
Eosinophils	Lactate dehydrogenase	Bilirubin
Basophils	Creatine kinase (CK)	Leukocyte esterase (LE)
	CK Isozymes MM	Nitrites
	CK Isozymes MB	Urobilinogen
	CK Isozymes BB	Additional urine microscopic variables ^a
	Troponin I, T	
	Myoglobin	
	Erythrocyte sedimentation rate	
	C-reactive protein	
	Total protein	
	Cholesterol (non-fasting)	
	Sodium	
	Potassium	
	Chloride	
	Bicarbonate	
	Magnesium	
	Calcium	
	Inorganic phosphate	
	IL – 6	
	IL – 1 Beta	

a. Additional urine microscopic variables include: amorphous crystals, bacteria, calcium carbonate crystals, calcium oxalate crystals, calcium phosphate crystals, cysteine crystals, granular casts, hyaline casts, leucine crystals, mucous, RBC, RBC casts, renal epithelial cells, squamous epithelial cells, transitional epithelial cells, triple phosphate crystals, tyrosine crystals, uric acid crystals, waxy casts, WBC, WBC casts, yeast.

Hematology, serum chemistry, and urinalysis will be summarized using descriptive statistics for numeric variables and numbers and percentages for categorical variables at each scheduled assessment. Numeric hematology, chemistry, and urinalysis results will be summarized using CFB as well. Shifts from baseline for clinical laboratory results will be summarized using the number and percentage of patients in each shift category.

Summaries by visit will include data from scheduled assessments, and all data will be reported according to the nominal visit date for which it was recorded.

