14.2.2 LABORATORY DATA TABLES

14.2.2.1.1 Hematology Results by Visit (Safety Population Cumulative)

Disease Study Visit	Parameter = Parameter 1 (units, if applicable)					
	Actual			Change from Baseline		
	N	Mean (SD)	Median (Min, Max)	N	Mean (SD)	Median (Min, Max)
Total (N = xx)						
Parent Study						
Baseline	xx	xx.x (xx.xx)	xx.x (xx, xx)			
Week 14/1-Week Follow-up	xx	xx.x (xx.xx)	xx.x (xx, xx)	xx	xx.x (xx.xx)	xx.x (xx, xx)
Current Study (ATYR1940-C-006)						
Week 1	xx	xx.x (xx.xx)	xx.x (xx, xx)	xx	xx.x (xx.xx)	xx.x (xx, xx)
Week 4	xx	xx.x (xx.xx)	xx.x (xx, xx)	xx	xx.x (xx.xx)	xx.x (xx, xx)
Week 8	xx	xx.x (xx.xx)	xx.x (xx, xx)	xx	xx.x (xx.xx)	xx.x (xx, xx)
...						
1-Week Post-treatment Follow-up	xx	xx.x (xx.xx)	xx.x (xx, xx)	xx	xx.x (xx.xx)	xx.x (xx, xx)
4-Week Post-treatment Follow-up	xx	xx.x (xx.xx)	xx.x (xx, xx)	xx	xx.x (xx.xx)	xx.x (xx, xx)
12-Week Post-treatment Follow-up	xx	xx.x (xx.xx)	xx.x (xx, xx)	xx	xx.x (xx.xx)	xx.x (xx, xx)
...						
<repeat for>						
EO-FSHD (N = xx)						
FSHD (N = xx)						
LGMD2B (N = xx)						

Note: FSHD=Facioscapulohumeral muscular dystrophy; LGMD2B=Limb-girdle muscular dystrophy 2B; EO-FSHD=Early Onset Facioscapulohumeral muscular dystrophy

Note: Baseline is defined as the baseline in the parent study.

Source: Listing xx.x.xx, Dataset: [NAME], Program: xxxxxx.sas, Output: T_14_2_2_1_1_XXXXX.rtf, Generated on: DDMMYYYY HH:MM

Page x of y

Programming Note: Baseline will be the last value prior to 1st ATYR1940 dose at Week 2 in the parent study. Labs collected due to the result of an IRR will not be summarized, but will be provided in the data listing. Parameters are listed in Section 9.6.2 of SAP text. Parameters should be presented in the same order as the protocol.

14.2.2.1.2 Shift Summary of Hematology Results by Reference Range and Visit (Safety Population Cumulative)

Parameter Study Visit Baseline Value	EO-FSHD (N = XX)				
	Post Baseline Value				
	Low	Normal	High	Total	Missing
Laboratory parameter 1					
Parent Study					
Week 14/1-Week Follow-up					
Low	xx (xx.x)	xx (xx.x)	xx (xx.x)	xx	xx
Normal	xx (xx.x)	xx (xx.x)	xx (xx.x)	xx	xx
High	xx (xx.x)	xx (xx.x)	xx (xx.x)	xx	xx
Total	xx (xx.x)	xx (xx.x)	xx (xx.x)	xx	xx
Missing	xx	xx	xx	xx	xx
Current Study (ATYR1940-C-006)					
Week 1					
Low	xx (xx.x)	xx (xx.x)	xx (xx.x)	xx	xx
Normal	xx (xx.x)	xx (xx.x)	xx (xx.x)	xx	xx
High	xx (xx.x)	xx (xx.x)	xx (xx.x)	xx	xx
Total	xx (xx.x)	xx (xx.x)	xx (xx.x)	xx	xx
Missing	xx	xx	xx	xx	xx
Week 4					

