14.2.2.2.1 Serum Chemistry Results by Visit (Safety Population Cumulative)

Programming Note: Repeat table 14.2.2.1.1. Parameters are listed in Section 9.6.2 of SAP text.

14.2.2.2.2 Shift Summary of Serum Chemistry Results by Reference Range and Visit (Safety Population Cumulative)

Programming Note: Repeat table 14.2.2.1.2. Parameters are listed in Section 9.6.2 of SAP text.

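### The SAP swaps the protocol's worst-CTCAE-grade laboratory shift tables for by-visit Low/Normal/High tables and has no count of clinically significant values, declaring neither change; its ADA and Jo-1 maximum tables also leave out reaction-triggered samples

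*SAP*

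**What the plan says.** **Laboratory tables.** Protocol 9.2.9 lists the analytes that need shift tables as a minimum: hemoglobin, white cells, neutrophils, lymphocytes, platelets, AST, ALT, total bilirubin, alkaline phosphatase, creatinine and electrolytes. On their form it says: "These tables will summarize the number of patients with each baseline CTCAE grade and changes to the maximum CTCAE grade on study". Just before that it says: "The frequency of clinically significant abnormal laboratory values will be tabulated".

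SAP 9.6.2 says only: "Shifts from baseline for clinical laboratory results will be summarized using the number and percentage of patients in each shift category". The shells in Appendix 5 settle what a shift category is. Table 14.2.2.1.2 is a "Shift Summary of Hematology Results by Reference Range and Visit (Safety Population Cumulative" and Table 14.2.2.2.2 a "Shift Summary of Serum Chemistry Results by Reference Range and Visit (Safety Population Cumulative". Both cross-tabulate Low, Normal and High at each visit. SAP 9.6.2 and the shell notes send IRR-triggered samples to listings only, and SAP 6.0 keeps unscheduled values out of tabulations generally. The SAP's stated use of CTCAE is for adverse events: "AE severity will be graded using Common Terminology Criteria for Adverse Events (CTCAE) version 4.03".

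**Antibody tables.** SAP 9.6.7 describes the ADA and Jo-1 tables as giving each patient's highest result. The same paragraph admits only samples from the defined collection times and sends IRR samples to listings. Tables 14.2.6.1 to 14.2.6.4 are titled as individual maxima and carry no footnote about this.

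**The concern.** Safety, tolerability and immunogenicity form the study's first objective. With up to 24 patients and no hypothesis tests, the descriptive tables are the analysis. A reader of the protocol expects to see how many patients moved from each baseline grade to each worst grade. The SAP's tables cannot answer that, and a reader of SAP 1.1 would not learn that the output had changed.

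The antibody tables raise a lesser version of the same problem: a summary labelled as a maximum is taken over a subset that leaves out samples drawn because of the main identified immune-type risk.

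**Working it through.** The plan has no sample-size calculation, alpha or power, so there is no figure to reproduce. The check sets the texts side by side and adds a few counts.

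**1. Commitments against outputs**

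| Protocol 9.2.9 laboratory output | SAP counterpart |
|---|---|
| Summary over time points | Kept (by-visit tables) |
| Change from baseline | Kept (numeric by-visit tables) |
| Frequency of clinically significant values | None |
| Baseline-to-maximum CTCAE grade shift | Replaced by reference-range shift at each visit |

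Of 4 outputs, 2 are kept, 1 is replaced and 1 has no counterpart. The six SAP laboratory tables are two each for hematology, chemistry and urinalysis. 0 of 6 uses a CTCAE grade and 0 of 6 counts clinically significant values. The separate PK/PD plan does not supply them either.

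**2. What the replacement loses**

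- *Grade.* Every grade above the range falls in one High cell. A patient who is High at baseline and worsens stays High-to-High; the same applies to Low.
- *Per-patient maximum.* For a patient treated 24 weeks, the shell gives parent Week 14 (1) + Weeks 1, 4, 8, 12, 16, 20, 24 (7) + three follow-ups (3) = up to 11 panels per analyte. These cannot be combined: if *a* patients are High at one visit and *b* at another, the number ever High lies anywhere between max(*a*, *b*) and *a* + *b*, capped at N.
- *Samples.* Protocol 8.5.9.4 calls for a full safety panel 1.5 to 2 hours after IRR onset, and Protocol 8.5.9.1 allows repeat tests at the investigator's choice. Neither enters a SAP laboratory table.

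**3. Whether adverse events fill the gap**

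Protocol 8.5.9.1 sends clinically significant laboratory changes to adverse-event reporting, and SAP Table 14.2.1.4 gives maximum grade per patient. But Protocol 8.5.10.1.1 says values the investigator judges not clinically significant should in general not be recorded as adverse events. Graded worsening of that kind would appear in no graded table. The protocol's shift table does not depend on that judgement.

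**4. Declaration**

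SAP 1.1 declares the baseline change ("However, the SAP defines baseline as the baseline in the parent study"), schedule clarifications and the age range. It does not mention the laboratory tables, and nor does the document history.

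**5. The antibody maxima**

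Let S be a patient's scheduled results and U the excluded ones. Then max(S) ≤ max(S ∪ U), so the tables can be too low but not too high. At least two kinds of sample are in U: the ADA and Jo-1 draws that SAP 1.1 itself sets at 1.5 to 2 hours after IRR onset.

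How often this changes a table depends on the other draws:

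- Over 24 weekly doses and full follow-up, scheduled ADA draws are 5 (Weeks 1, 6, 12, 18, 24) + 3 = 8, and Jo-1 draws are 24 + 3 = 27.
- An IRR ends dosing (Protocol 6.4.1), and the 1-week follow-up (±3 days) draws both. An IRR sample is lost as a maximum only if it exceeds every earlier scheduled value and all three follow-up values.
- Jo-1 is also drawn before the same infusion, so there is little room for a difference.
- The ADA listing maps results to 8 titers (41, 82, 164, 328, 656, 1312, 2624, 5248), which gives 7 adjacent steps. Only 328 to 656 and 2624 to 5248, 2 of 7, cross a column of the table. This shows how coarse the table is, not how likely an error is.

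**The case against.** Several points on the other side stand.

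- A reader might infer that laboratory shift analysis has been dropped. It has not. The SAP's shift tables cover all hematology and chemistry parameters, which is wider than the protocol's minimum list, and Listing 16.2.10 shows every value with its change from baseline, normal range and flag.
- A reader might call the silence in SAP 1.1 a protocol breach. Protocol 9.2 calls itself an overview with details left to the SAP, and Protocol 9.3 says: "Changes to the planned statistical methods will be documented in the clinical study report". The silence is a documentation gap, though in the very section meant for such changes.
- A reader might say the antibody exclusion is hidden or contradicts the protocol. It is stated openly in SAP 9.6.7 and conflicts with no protocol sentence. The fault is the mismatch with the titles and the stated content.
- A reader might say the repeat ADA tests after a raised 12-week value are excluded too. SAP 9.6.7 does not list them, but footnote 19 of the SAP's own schedule specifies them every 1 to 3 months, so their status is unclear. The 12-week visit is also end of study, and nothing says later results reach this database.
- A reader might count extra visits after dosing stops as lost samples. The documents do not say what is drawn there. Protocol 7.5.5.2 has patients who reach the Jo-1 threshold return per protocol if feasible, and SAP 9.6.7 lists Jo-1 weekly, so those samples may count as scheduled.
- Scheduled dosing-day antibody samples are pre-infusion, while IRR draws follow drug administration by hours, with a half-life of about 3 to 6 hours. Keeping the two apart is defensible, but then the label should say so.

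None of this supplies the worst-grade table or the clinically significant count.

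**Conclusion.** The laboratory point holds: two protocol outputs are changed without declaration, one replaced and one left without a counterpart, and no planned table gives a patient's worst laboratory grade. This limits what the safety tables can show. It does not mean abnormal values go unrecorded.

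The antibody point holds in smaller form. Four tables can understate a maximum. The effect is probably small, more plausible for ADA than for Jo-1, and its size cannot be derived because the documents give no IRR rate or antibody time course for this study. The excluded results remain in Listings 16.2.17.1 and 16.2.17.2 with an IRR flag.

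The conclusion assumes that the shells are what will be programmed and that no other analysis plan, outside the documents available, supplies the missing tables. It should be corrected before the final tables are run.

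**What to change.** (a) Add the baseline-to-maximum-CTCAE-grade shift tables for the analytes named in Protocol 9.2.9. Use all post-baseline values, including unscheduled and IRR-triggered ones, and state whether the study period means the extension alone or parent plus extension.

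(b) Compute Tables 14.2.6.1 to 14.2.6.4 from all post-baseline samples in the database within each table's data scope. Otherwise, retitle and footnote them as the maximum of scheduled samples. Either way, state how ADA repeats after the 12-week visit are treated.

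(c) Tabulate clinically significant laboratory values if that judgement is captured. Listing 16.2.10 shows a range flag but no such column, and the CRF is not among the documents, so this may not be possible. If not, declare the departure in SAP 1.1.

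Leave the by-visit tables on scheduled data; that rule suits them.

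Cost: SAP wording, CTCAE grading of laboratory values already collected, and a few table programs. Parts (a) and (b), confined to what is in the database, need no new data. SAP 1.0 provides for a final version before database lock, which is the natural place for the change. The downside is a little extra programming and worst-case tables that may look slightly less favourable.

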14.2.2.2.1 Serum Chemistry Results by Visit (Safety Population Cumulative)

Programming Note: Repeat table 14.2.2.1.1. Parameters are listed in Section 9.6.2 of SAP text.

14.2.2.2.2 Shift Summary of Serum Chemistry Results by Reference Range and Visit (Safety Population Cumulative)

Programming Note: Repeat table 14.2.2.1.2. Parameters are listed in Section 9.6.2 of SAP text.

14.2.2.3.1 Quantitative Urinalysis Results by Visit (Safety Population Cumulative)

Programming Note: Repeat table 14.2.2.1.1. Parameters are listed in Section 9.6.2 of SAP text; this table is for quantitative parameters only.

14.2.2.3.2 Qualitative Urinalysis Results by Visit (Safety Population Cumulative)

Parameter Study Visit Category	EO-FSHD (N = XX) n (%)	FSHD (N = XX) n (%)	LGMD2B (N = XX) n (%)	Total (N = XX) n (%)
Laboratory parameter 1 (unit)				
Parent Study				
Baseline	xx	xx	xx	xx
Normal	xx (xx.x)	xx (xx.x)	xx (xx.x)	xx (xx.x)
Abnormal	xx (xx.x)	xx (xx.x)	xx (xx.x)	xx (xx.x)
Week 14/1-Week Follow-up	xx	xx	xx	xx
Normal	xx (xx.x)	xx (xx.x)	xx (xx.x)	xx (xx.x)
Abnormal	xx (xx.x)	xx (xx.x)	xx (xx.x)	xx (xx.x)
Current Study (ATYR1940-C-006)				
Week 1	xx	xx	xx	xx
Normal	xx (xx.x)	xx (xx.x)	xx (xx.x)	xx (xx.x)
Abnormal	xx (xx.x)	xx (xx.x)	xx (xx.x)	xx (xx.x)
Week 4	xx	xx	xx	xx
Normal	xx (xx.x)	xx (xx.x)	xx (xx.x)	xx (xx.x)
Abnormal	xx (xx.x)	xx (xx.x)	xx (xx.x)	xx (xx.x)
...				
12-Week Post-treatment Follow-up				
...				

Note: FSHD=Facioscapulohumeral muscular dystrophy; LGMD2B=Limb-girdle muscular dystrophy 2B; EO-FSHD=Early Onset Facioscapulohumeral muscular dystrophy

Note: Percentage based on the number of non-missing evaluations for each parameter and time point.

Note: Abnormal is defined as values beyond the normal ranges.

Source: Listing xx.x.xx, Dataset: [NAME], Program: xxxxx.sas, Output: T_14_2_2_3_2_XXXXX.rtf, Generated on: DDMMMYYYY HH:MM

Page x of y

Programming Note: Parameters are listed in Section 9.6.2 of SAP text. Baseline will be the last value prior to 1st ATYR1940 dose at Week 2 in the parent study. Parameters should be presented in the same order as the protocol. Labs collected due to the result of an IRR will not be summarized, but will be provided in the data listing.

14.2.3 ELECTROCARDIOGRAM DATA TABLES

14.2.3.1 Electrocardiogram Results by Visit (Safety Population Cumulative)

Disease Study Visit	Parameter = Parameter 1 (units, if applicable)								
	Actual			Change From Baseline			Change from Pre-infusion		
	N	Mean (SD)	Median (Min, Max)	N	Mean (SD)	Median (Min, Max)	N	Mean (SD)	Median (Min, Max)
Total (N = xx)									
Parent Study									
Baseline	xx	xx.x (xx.xx)	xx.x (xx, xx)						
Week 14/1-Week Follow-up	xx	xx.x (xx.xx)	xx.x (xx, xx)	xx	xx.x (xx.xx)	xx.x (xx, xx)			
Current Study (ATYR1940-C-006)									
Week 1 (pre-infusion)	xx	xx.x (xx.xx)	xx.x (xx, xx)	xx	xx.x (xx.xx)	xx.x (xx, xx)			
Week 1 (30 min post-infusion)	xx	xx.x (xx.xx)	xx.x (xx, xx)	xx	xx.x (xx.xx)	xx.x (xx, xx)	xx	xx.x (xx.xx)	xx.x (xx, xx)
Week 4 (pre-infusion)	xx	xx.x (xx.xx)	xx.x (xx, xx)	xx	xx.x (xx.xx)	xx.x (xx, xx)			
Week 4 (30 min post-infusion)	xx	xx.x (xx.xx)	xx.x (xx, xx)	xx	xx.x (xx.xx)	xx.x (xx, xx)	xx	xx.x (xx.xx)	xx.x (xx, xx)
Week 8 (pre-infusion)	xx	xx.x (xx.xx)	xx.x (xx, xx)	xx	xx.x (xx.xx)	xx.x (xx, xx)			
Week 8 (30 min post-infusion)	xx	xx.x (xx.xx)	xx.x (xx, xx)	xx	xx.x (xx.xx)	xx.x (xx, xx)	xx	xx.x (xx.xx)	xx.x (xx, xx)
Week 12 (pre-infusion)	xx	xx.x (xx.xx)	xx.x (xx, xx)	xx	xx.x (xx.xx)	xx.x (xx, xx)			
Week 12 (30 min post-infusion)	xx	xx.x (xx.xx)	xx.x (xx, xx)	xx	xx.x (xx.xx)	xx.x (xx, xx)	xx	xx.x (xx.xx)	xx.x (xx, xx)
...									
1-Week Post-treatment Follow-up	xx	xx.x (xx.xx)	xx.x (xx, xx)	xx	xx.x (xx.xx)	xx.x (xx, xx)			
4-Week Post-treatment Follow-up	xx	xx.x (xx.xx)	xx.x (xx, xx)	xx	xx.x (xx.xx)	xx.x (xx, xx)			
...									
<repeat for>									
EO-FSHD (N = xx)									
FSHD (N = xx)									
LGMD2B (N = xx)									

Note: FSHD=Facioscapulohumeral muscular dystrophy; LGMD2B=Limb-girdle muscular dystrophy 2B; EO-FSHD=Early Onset Facioscapulohumeral muscular dystrophy

Note: Baseline is defined as the baseline in the parent study.

Note: Change from Pre-infusion = post-infusion time point – pre-infusion.

Source: Listing xx.x.xx, Dataset: [NAME], Program: xxxxxx.sas, Output: T_14_2_3_1_XXXXX.rtf, Generated on: DDMMYYYY HH:MM

Page x of y

Programming Note: Baseline will be the last value prior to 1st ATYR1940 dose at Week 2 in the parent study (pre-infusion at Week 2). Assessments collected due to the result of an IRR will not be summarized, but will be provided in the data listing. Parameters are heart rate (beats/min), P-R interval (msec), QRS interval (msec), QT interval (msec), QTcB, QTcF, R-R interval (msec).

